8.5 Procedures to be Followed in the Event of Abnormal Laboratory Test Values

Any Grade 2 or higher abnormal laboratory value will be reported as an AE, regardless of the relationship to the study product or clinical significance. Grade 1 laboratory abnormalities will be reported as AEs if assessed by the investigator as related to the study product. Laboratory abnormalities reported as AEs will be followed until the abnormality stabilizes, normalizes or returns to a baseline level, whichever comes first, at the discretion of the investigator.

In the approach to grading laboratory values, if the Lower Limit of Normal (LLN) entered at the site falls within CTCAE defined graded values, the CTCAE ranges will be used to grade an AE, rather than using local laboratory ranges for determining normal and abnormal laboratory values.

Intermittent abnormal laboratory values such as electrolyte abnormalities or blood glucose levels that are part of the same clinical diagnosis (e.g., uncontrolled diabetes) can be recorded once with the highest grade for each fluctuating AE (Grade 2 or higher for this trial), including the start and stop dates of the intermittent syndrome. If the event has a clear resolution for a duration of at least 48 hours and then recurs, it should be treated as a separate AE. An AE resolution is defined as return to pre-treatment status or baseline for duration of more than 48 hours.

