## 4.5. Primary Endpoint Variables

The three primary objectives are as follows: (1) the safety of a single dose of IV bacteriophage therapy in clinically stable CF subjects with *P. aeruginosa* in expectorated sputum, (2) the microbiological activity of a single dose of IV bacteriophage therapy in clinically stable CF subjects with *P. aeruginosa* in expectorated sputum, and (3) the benefit to risk profile of a single dose of IV bacteriophage therapy in clinically stable CF subjects with *P. aeruginosa* in expectorated sputum.

The safety endpoint will be measured by the number of Grade 2 or higher treatment-emergent AEs through Day  $30 \pm 7$ . Safety will also be assessed through the incidence of treatment-emergent adverse events (TEAEs), on-therapy SAEs, and AEs leading to premature discontinuation. Adverse events will be graded according to the Common Terminology Criteria for Adverse Events (CTCAE) Version 5.0, November 2017 ([https://ctep.cancer.gov/protocoldevelopment/electronic\\_applications/ctc.htm#ctc\\_50](https://ctep.cancer.gov/protocoldevelopment/electronic_applications/ctc.htm#ctc_50)). Details about adverse event grading and determination of relationship to study product can be found in the protocol, Section 8.1.1.1.

Clinical laboratory results, including chemistry, hematology, and liver function tests, will also be graded according to the CTCAE scale. Clinical chemistry parameters include serum creatinine, blood urea nitrogen (BUN), glucose, sodium, potassium, chloride, bicarbonate, and calcium. Hematology parameters include complete blood count with red blood cell (RBC) count, hemoglobin, hematocrit, total white blood cell (WBC) count with differential counts, and platelet count. Liver function tests include aspartate aminotransferase (AST), alanine aminotransferase (ALT), alkaline phosphatase, total bilirubin, lactate dehydrogenase, albumin, and total protein. Only AST, ALT, and total bilirubin are collected at Screening. Clinical chemistry, hematology, and liver function tests will be performed at baseline and at follow-up visits occurring on Days 2, 5, 8, 12 (Stage 1 only), and 30. Refer to Section 3.3.2 for the definition of baseline.

The microbiological activity endpoint will be measured based on the change in  $\log_{10}$  *P. aeruginosa* colony counts after administration of IV bacteriophages/placebo. Sputum collection for measuring colony counts will occur at baseline and at follow-up visits occurring on Days 2, 5, 8, and 30.

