### 9.6. Clinical Laboratory Evaluations

After Protocol v5.0, Visit 6 (Study Day 12 + 7) was removed from the visit schedule for any subjects enrolling in Stage 2a or Stage 2b. Any laboratory summaries for Day 12 data will only show data from Stage 1 subjects. Any laboratory data collected during this visit for Stage 2a subjects who enrolled under the previous version of the Protocol will be included in lab listings only.

The distribution of laboratory results will be presented by severity, time point, and treatment group. Clinical chemistry parameters will be displayed beginning with [Table 63](#) and continuing through [Table 71](#), hematology parameters will be displayed beginning with [Table 80](#) and continuing through [Table 88](#), and liver function tests parameters will be displayed beginning with [Table 97](#) and continuing through [Table 104](#). Descriptive statistics, including mean, SD, median, minimum, maximum, and change from baseline by time point and treatment group will be presented beginning with [Table 72](#) and continuing through [Table 79](#) for clinical chemistry parameters, beginning with [Table 89](#) and continuing through [Table 96](#) for hematologic parameters, and beginning with [Table 105](#) and continuing through [Table 111](#) for liver function test parameters.

Graphical presentations of change from baseline at scheduled visits by treatment group and time point for each parameter as a series of box plots. Chemistry parameters will be presented beginning with [Figure 20](#) and continuing through [Figure 27](#). Hematology parameters will be presented beginning with [Figure 28](#) and continuing through [Figure 35](#). Liver function parameters will be presented beginning with [Figure 36](#) and continuing through [Figure 42](#).

Abnormal chemistry results will be presented in [Table 60](#), abnormal hematologic results will be presented in [Table 61](#), and abnormal liver function results will be presented in [Table 62](#).

All chemistry results will be presented in [Listing 18](#), all hematologic results will be presented in [Listing 19](#) and all liver function results will be presented in [Listing 20](#).

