**Table 62: Listing of Abnormal Laboratory Results – Liver Function Tests**

[Implementation Note: This listing is included in the table shells document, as it is included in the body of the CSR. This listing should include all urinalysis results for any subject that had at least one abnormal urinalysis laboratory result. A complete listing of all laboratory results is included in the listings document. In the Laboratory Parameter column, indicate the units after the parameter, e.g., Hemoglobin (g/dL). This listing is not color-coded, but the severity should be included in parentheses after the result, e.g., 16.2 (mild). In the “If Not Related, Alternate Etiology” column, merge the 2 data fields for collecting alternate etiology, separate by a colon. In the CSR, Subject ID should be USUBJID (not PATID) for purposes of de-identification.]

Subject ID	Treatment Group	Sex	Age (years)	Planned Time Point	Actual Study Day	Laboratory Parameter (Units)	Result (Severity)	Relationship to Treatment	If Not Related, Alternate Etiology	Action Taken with Study Treatment	Subject Discontinued Due to Result?

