### 14.3.5 Displays of Laboratory Results

#### 14.3.5.1 Chemistry Results

**Table 63: Chemistry Laboratory Results by Parameter, Maximum Severity, Time Point, and Treatment Group – Any Chemistry Parameter**

[Implementation note: If no missing or outside normal range (ONR) results are reported, these columns will not be included, and corresponding footnotes should be removed. If parameter is not graded then only ‘Within Normal Range’, ‘Outside Normal Range’, and ‘Missing’ columns will be included.]

Treatment group order: All subjects,  $4 \times 10^7$  PFU Dose,  $4 \times 10^8$  PFU Dose,  $4 \times 10^9$  PFU Dose, Placebo.]

Time Point	Treatment Group	N	None		Outside Normal Range a		Mild/ Grade 1		Moderate/ Grade 2		Severe/ Grade 3		Missing	
			n	%	n	%	n	%	n	%	n	%	n	%
Stage 1														
Baseline	All Subjects (N=X)	x	x	xx	x	xx	x	xx	x	xx	x	xx	x	xx
	...													
	Placebo	x	x	xx	x	xx	x	xx	x	xx	x	xx	x	xx
Day 2	All Subjects (N=X)	x	x	xx	x	xx	x	xx	x	xx	x	xx	x	xx
	...													
Day 5	All Subjects (N=X)	x	x	xx	x	xx	x	xx	x	xx	x	xx	x	xx
	...													
Day 8	All Subjects (N=X)	x	x	xx	x	xx	x	xx	x	xx	x	xx	x	xx
	...													
Day 12 b	All Subjects (N=X)	x	x	xx	x	xx	x	xx	x	xx	x	xx	x	xx
	...													
Day 30	All Subjects (N=X)	x	x	xx	x	xx	x	xx	x	xx	x	xx	x	xx
	...													
Max Severity Post Baseline	All Subjects (N=X)	x	x	xx	x	xx	x	xx	x	xx	x	xx	x	xx
	...													

**Table 63: Chemistry Laboratory Results by Parameter, Maximum Severity, Time Point, and Treatment Group – Any Chemistry Parameter (continued)**

Time Point	Treatment Group	N	None		Outside Normal Range a		Mild/ Grade 1		Moderate/ Grade 2		Severe/ Grade 3		Missing	
			n	%	n	%	n	%	n	%	n	%	n	%
Stage 2a														
...														
Stage 2a and 2b														
...														

Notes: The “Max Post Baseline” rows indicate the maximum severity experienced by each subject at any time point post baseline, including unscheduled assessments.

N=Number of subjects in the Safety Population

aPost-dose measurements that were outside the normal range but did not meet the definition for an AE due to the value being less than or equal to the measurement at baseline will be categorized as “Outside Normal Range”

bOnly data from Stage 1 subjects will be summarized for this visit. Any Stage 2a subjects with Day 12 data will be included only in lab listings.

Tables with similar format:

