Time Point	Treatment Group	N	None		Outside Normal Range a		Mild/ Grade 1		Moderate/ Grade 2		Severe/ Grade 3		Missing	
			n	%	n	%	n	%	n	%	n	%	n	%
Stage 2a														
...														
Stage 2a and 2b														
...														

Notes: The “Max Post Baseline” rows indicate the maximum severity experienced by each subject at any time point post baseline, including unscheduled assessments.

N=Number of subjects in the Safety Population

aPost-dose measurements that were outside the normal range but did not meet the definition for an AE due to the value being less than or equal to the measurement at baseline will be categorized as “Outside Normal Range”

bOnly data from Stage 1 subjects will be summarized for this visit. Any Stage 2a subjects with Day 12 data will be included only in lab listings.

Tables with similar format:

- Table 81: Hematology Laboratory Results by Parameter, Maximum Severity, Time Point, and Treatment Group – RBC**
- Table 82: Hematology Laboratory Results by Parameter, Maximum Severity, Time Point, and Treatment Group – Hemoglobin**
- Table 83: Hematology Laboratory Results by Parameter, Maximum Severity, Time Point, and Treatment Group – Hematocrit**
- Table 84: Hematology Laboratory Results by Parameter, Maximum Severity, Time Point, and Treatment Group – WBC**
- Table 85: Hematology Laboratory Results by Parameter, Maximum Severity, Time Point, and Treatment Group – Platelets**
- Table 86: Hematology Laboratory Results by Parameter, Maximum Severity, Time Point, and Treatment Group – Neutrophils**
- Table 87: Hematology Laboratory Results by Parameter, Maximum Severity, Time Point, and Treatment Group – Lymphocytes**
- Table 88: Hematology Laboratory Results by Parameter, Maximum Severity, Time Point, and Treatment Group – Monocytes**

**Table 89: Hematology Laboratory Summary Statistics by Parameter, Time Point, and Treatment Group – RBC**[Implementation note: Treatment group order: All subjects, 4 x 10^7 PFU Dose, 4 x 10^8 PFU Dose, 4 x 10^9 PFU Dose, Placebo.]

Time Point	Treatment Group	Laboratory Value (Units)					Change from Baseline (Units)				
		n	Mean	Standard Deviation	Median	Min, Max	n	Mean	Standard Deviation	Median	Min, Max
Stage 1											
Baseline	All Subjects (N=X)	x	xx.x	xx.x	xx	xx, xx	-	-	-	-	-
	...										
	Placebo (N=X)	x	xx.x	xx.x	xx	xx, xx	-	-	-	-	-
Day 2	All Subjects (N=X)	x	xx.x	xx.x	xx	xx, xx	x	xx.x	xx.x	xx	xx, xx

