**Table 102: Liver Function Laboratory Results by Parameter, Maximum Severity, Time Point, and Treatment Group – Albumin**

**Table 103: Liver Function Laboratory Results by Parameter, Maximum Severity, Time Point, and Treatment Group – Lactate Dehydrogenase**

**Table 104: Liver Function Laboratory Results by Parameter, Maximum Severity, Time Point, and Treatment Group – Total Protein**

**Table 105: Liver Function Laboratory Summary Statistics by Parameter, Time Point, and Treatment Group – Aspartate Aminotransferase**[Implementation note: Treatment group order: All subjects, 4 x 10^7 PFU Dose, 4 x 10^8 PFU Dose, 4 x 10^9 PFU Dose, Placebo.]

Time Point	Treatment Group	Laboratory Value (Units)					Change from Baseline (Units)				
		n	Mean	Standard Deviation	Median	Min, Max	n	Mean	Standard Deviation	Median	Min, Max
Stage 1											
Baseline	All Subjects (N=X)	x	xx.x	xx.x	xx	xx, xx	-	-	-	-	-
	...										
	Placebo (N=X)	x	xx.x	xx.x	xx	xx, xx	-	-	-	-	-
Day 2	All Subjects (N=X)	x	xx.x	xx.x	xx	xx, xx	x	xx.x	xx.x	xx	xx, xx
	...										
	Placebo (N=X)	x	xx.x	xx.x	xx	xx, xx	x	xx.x	xx.x	xx	xx, xx
Day 5	All Subjects (N=X)	x	xx.x	xx.x	xx	xx, xx	x	xx.x	xx.x	xx	xx, xx
	...										
	Placebo (N=X)	x	xx.x	xx.x	xx	xx, xx	x	xx.x	xx.x	xx	xx, xx
Day 8	All Subjects (N=X)	x	xx.x	xx.x	xx	xx, xx	x	xx.x	xx.x	xx	xx, xx
	...										
	Placebo (N=X)	x	xx.x	xx.x	xx	xx, xx	x	xx.x	xx.x	xx	xx, xx
Day 12 a	All Subjects (N=X)	x	xx.x	xx.x	xx	xx, xx	x	xx.x	xx.x	xx	xx, xx
	...										
	Placebo (N=X)	x	xx.x	xx.x	xx	xx, xx	x	xx.x	xx.x	xx	xx, xx
Day 30	All Subjects (N=X)	x	xx.x	xx.x	xx	xx, xx	x	xx.x	xx.x	xx	xx, xx
	...										
	Placebo (N=X)	x	xx.x	xx.x	xx	xx, xx	x	xx.x	xx.x	xx	xx, xx

**Table 105: Liver Function Laboratory Summary Statistics by Parameter, Time Point, and Treatment Group – Aspartate Aminotransferase (continued)**

Time Point	Treatment Group	Laboratory Value (Units)					Change from Baseline (Units)				
		n	Mean	Standard Deviation	Median	Min, Max	n	Mean	Standard Deviation	Median	Min, Max
Stage 2a											
...											
Stage 2a and 2b											
...											

Notes: N=Number of subjects in the Safety Population.

n=Number of subjects in the Safety Population with non-missing laboratory values at the time point of interest. For the change from baseline, n represents the number of subjects in the Safety Population with non-missing values at baseline and at the time point being assessed.

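### Lab severity tables: footnote a leaves an out-of-range result ungraded because it is at or below baseline, which is backwards for graded tests whose abnormality is a fall

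*SAP*

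**What the plan says.** SAP 4.5 commits to grading all three laboratory panels: "Clinical laboratory results, including chemistry, hematology, and liver function tests, will also be graded according to the CTCAE scale". SAP 9.6 then tabulates results by severity, time point and treatment group.

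The shells for these tables have columns for none, Outside Normal Range, Grades 1 to 3, and missing. Footnote a defines the second column. It holds post-dose results outside the normal range that "did not meet the definition for an AE due to the value being less than or equal to the measurement at baseline". The same sentence stands under Table 63 (chemistry), Table 80 (hematology) and Table 97 (liver function). Each shell is reused for single-parameter tables, among them "Hematology Laboratory Results by Parameter, Maximum Severity, Time Point, and Treatment Group – Hemoglobin" (Table 82) and "Liver Function Laboratory Results by Parameter, Maximum Severity, Time Point, and Treatment Group – Albumin" (Table 102). The maximum post-baseline severity row uses the same columns. An implementation note removes the grade columns for any parameter that is not graded.

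Protocol 8.5 uses a different criterion: "Any Grade 2 or higher abnormal laboratory value will be reported as an AE", whatever its relationship to study product or clinical significance. The same section says which ranges to use "if the Lower Limit of Normal (LLN) entered at the site falls within CTCAE defined graded values", so low values are meant to be graded. Protocol 8.1.1 counts a pre-existing condition as an AE when its frequency or severity increases. Protocol 10.5.9 and SAP 8.1.1 define a treatment-emergent event with prior presence by increased severity.

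**The concern.** The footnote decides whether a result is graded by comparing raw numbers, and it treats a lower number as no worse. That is right for a transaminase or creatinine. It is wrong for hemoglobin, platelets, white cells, neutrophils or albumin, and for the low side of sodium, potassium, calcium or glucose. No AE definition in either document contains such a criterion.

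Safety is a primary objective, and these are the tables that show graded laboratory findings by dose and visit. If they are programmed as printed, a new cytopenia would sit in an ungraded column while a low value on its way back to normal could appear as a graded post-dose finding.

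**Working it through.** The plan gives no figure to reproduce; this is a check of a classification rule.

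**Inputs.** Let *b* be baseline, *p* the post-dose value, and L and U the lower and upper limits of normal. Footnote a, read literally, says: if *p* is outside [L, U] and *p* ≤ *b*, show Outside Normal Range; if *p* is outside [L, U] and *p* > *b*, grade it.

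**Cases.**

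| Situation | Ordering | Footnote a | Judged by severity |
|---|---|---|---|
| New fall from normal | *p* < L ≤ *b*, so *p* < *b* | ungraded | should be graded |
| Low baseline, falls to a worse grade | *p* < *b* < L | ungraded | should be graded |
| Low baseline, partial recovery | *b* < *p* < L | graded | not a worsening |
| New rise from normal | *b* ≤ U < *p* | graded | should be graded |
| High baseline, partial recovery | U < *p* < *b* | ungraded | not a worsening |

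The first row has no exceptions: a value below L cannot exceed a baseline at or above L. The rule is correct in both high-side rows and wrong in all three low-side rows.

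**Illustration.** The documents give no reference ranges. Assume a hemoglobin lower limit above 8.5 and no higher than 13.0 g/dL. A fall from 13.0 to 7.5 satisfies 7.5 ≤ 13.0 and is not graded. A rise from 7.5 to 8.5 gives 8.5 > 7.5 and is graded.

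**Simulation check.** The assumptions are a unit-free analyte, normal range ±1.96, baseline SD 1.2, noise SD 0.7, mean shifts of 0.5, 1, 2 and 3, and 400,000 draws each.

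- Mean fall of 0.5: 39,985 new low results, 0% graded; 2,650 improved but still low, 100% graded.
- Mean fall of 2: 184,286 new low results, 0% graded; 34 improved but still low, 100% graded.
- Mean fall of 3: 288,010 new low results, 0% graded; none improved while still low.
- Mean rise of 0.5: 40,475 new high results, 100% graded; 2,681 improved but still high, 0% graded.

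The remaining settings give the same shares. Because the simulation codes the literal rule, it confirms the algebra and says nothing about how often such falls will occur in this trial.

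**Reach of the wording.** Tables 63–71, 80–88 and 97–104 number 9 + 9 + 8 = 26. Three of these are any-parameter tables, leaving 23 single-parameter tables. This is how far the footnote is carried, not a count of tests it misclassifies.

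**The case against.** The best defence is that the footnote has a first condition: the result must not have met the definition of an AE. Protocol 8.5 makes every Grade 2 or higher value an AE, so a serious fall would be excluded from the Outside Normal Range column by the footnote's own terms and would be graded. This reading is available, and it makes the literal reading one of two. It does not rescue the footnote. Under Protocol 8.1.1 and 8.5, Grade 1 abnormalities are recorded as AEs only if judged related, so unrelated Grade 1 falls would still be misfiled. The stated reason, a raw value at or below baseline, also remains wrong for falls, and it is the part a programmer can code.

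It can also be said that little depends on these tables. That largely stands. A reader might infer that new falls would be invisible and the laboratory safety report falsely clean. The documents do not support that. Tables 44–45 rest on reported AEs. Tables 60–61 print severity beside each result, and Listings 18–20 give every result with its grade. Tables 72–79, 89–96 and 105–111 show change from baseline by group. The halting rules in Protocol 8.6.1 turn on AEs and pulmonary exacerbations, not on these tables.

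A reader might also see a second fault in SAP 9.6, where Day 12 results "for Stage 2a subjects who enrolled under the previous version of the Protocol will be included in lab listings only" and so drop out of the maximum-severity row. That is an explained choice: the visit was removed for Stage 2 after Protocol v5.0. Restoring those results would make ascertainment unequal, because in the pooled Stage 2a and 2b block the placebo and selected-dose arms gain Stage 2b subjects with no Day 12 visit, while the dropped doses do not.

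The Table 62 instruction, "This listing should include all urinalysis results for any subject that had at least one abnormal urinalysis laboratory result", is template carry-over. No urinalysis panel is collected, and both the table title and SAP 9.6 say liver function.

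**Conclusion.** The point holds for graded parameters with a low-side abnormality. On the literal reading, every new low result from a normal baseline goes ungraded and every partial recovery that stays low is graded, in the by-visit and maximum-severity laboratory tables. On the narrower reading, the error is confined to lower-grade falls, but the printed reason is still wrong.

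Two broader claims are tempting and not supported. One is a count of affected tests: which parameters CTCAE grades on the low side is not reproduced in either document, and an ungraded parameter has no grade column to lose. The other is that every worsening is misclassified: for tests graded in both directions, such as glucose or potassium, new rises are handled correctly.

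The conclusion assumes that the tests named above as examples are graded on the low side. It should be corrected before the tables are programmed. The primary safety analysis does not depend on it.

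**What to change.** Replace footnote a in Tables 63, 80 and 97, and in the tables built on them, with wording such as: *A post-dose result outside the normal range is shown as Outside Normal Range, without a grade, only when its CTCAE grade in the same direction of abnormality is no higher than the baseline grade in that direction.* A normal baseline counts as no grade.

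New falls and falls to a worse grade would then be graded, and partial recoveries would not. New rises from a normal baseline stay graded. One high-side change follows: a value that rises within its baseline grade moves out of the grade columns.

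Reconcile this with Protocol 8.5. A result that is Grade 2 both at baseline and after dosing is reportable as an AE under a literal reading of 8.5, but would be shown as Outside Normal Range here. State that these tables show worsening in grade and do not determine AE status, or state which rule governs.

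Leave the Day 12 handling as it is. As clerical clean-up, make Table 62 select and print liver function results, and make Table 60 print chemistry results for subjects selected on chemistry.

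The cost is one footnote, one derivation rule and two shell notes, with no new data.

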**Table 66: Chemistry Laboratory Results by Parameter, Maximum Severity, Time Point, and Treatment Group – Glucose**

**Table 67: Chemistry Laboratory Results by Parameter, Maximum Severity, Time Point, and Treatment Group – Sodium**

**Table 68: Chemistry Laboratory Results by Parameter, Maximum Severity, Time Point, and Treatment Group – Potassium**

